Interventionist Training and Tracking: The interventionist will have a degree in a health-related field such as psychology or nursing. They will be trained in ENRICH/ECHO, an oncofertility communication training program. This training program include several modules to assist oncology health professionals

effectively communicate key information regarding reproductive health to AYA. Additionally, the interventionist will be extensively trained in the use of the FP Decision Tool, the interactive report, and the communication intervention by Drs. [name] and [name].

Intervention Fidelity: Consistent delivery of the study interventions will be monitored throughout the intervention phase of the study. A random selection of audiotapes of the interactions will be reviewed by trained research staff on an ongoing basis who will complete a checklist of the five points to be covered in the facilitated conversation to monitor intervention fidelity. The five points are: 1) address knowledge gaps/misconceptions by referring families back to the fertility navigator, 2) share participants' fertility-related values and goals with one another, 3) highlight discrepancies between responses, and 4) promote family communication and consensus building.

*Not applicable if only one family member is participating.

6.0 **Procedures Involved***

Study Design: This single-site study is an RCT of a family-centered psychoeducational decision tool intervention. Participants will be male AYA (ages 12-25-years) newly diagnosed with cancer and their caregivers. Families will be randomized (1:1) to either receive 1) standard of care fertility consult or 2) standard of care fertility consult + the family-centered psychoeducational decision tool and facilitated communication.

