- *Brief Subjective Decision Quality measure (BSDQ):* A six-item scale used to measure decision satisfaction and administered to AYA and both parents. Item will be scored into a composite decision satisfaction score (0-7).
- *The Parent-Adolescent Communication Scale (PACS):* A twenty-item scale used to measure perceived communication between AYA and parents will be administered to AYA and both parents. AYA will rate communication with both mother and father. Parents will only rate communication with son. Item scored into three scales: openness, problems, and a composite communication score.
- *Parenthood Goals Survey:* A sixteen-item survey used to examine parental and AYA views on parenthood. This survey is a modified version of the FP Decision Tool. This survey will be given to families in both the control and intervention group.
- *Feasibility and Acceptability Survey:* For the intervention group only, AYA and parents will fill out a twelve-item scale that will be used to assess satisfaction with the intervention structure and

content. The scale will include a final open-ended question asking for comments/suggestions about the intervention. The parent survey will include an additional item specific to how the intervention helped them help their child.

• *Brief Interview:* Study staff will also complete a brief, 15-minute semi-structured interview separately with each participant. The interview will focus on what participants discussed in relation to FP, how they made their decision, how they feel about their decision, and how they feel overall about their fertility counseling experience. The final question will give families the opportunity to share any additional thoughts. Interviews will take place away from other participants to allow each interviewee to speak freely. Interviews will be audio recorded and transcribed verbatim and coded for thematic content by trained research staff.

1-year Follow-up (Visit 3, Baseline + 1-year (+/- 1 month): At the 1-year follow-up (Visit 3) research staff will contact control and intervention families in-person (at inpatient or outpatient clinic) or via phone or email. Families (AYAs and parents) will be reminded about the study and research activities. All measures will be completed by the child and both caregivers (when available). The activities completed at Visit 3 include:

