12.0 Local Number of Subjects

This study will enroll 40 male AYAs and 70 caregivers, at the single-site, Nationwide Children's Hospital. There are approximately 30 males newly diagnosed with cancer in our target age range each year. Taking into account our inclusion/exclusion criteria, infrastructure of the fertility consult service, and recruitment rates in our pilot (>90%), we anticipate completing our recruitment goals within the allocated timeframe.

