17.0 Data Management* and Confidentiality

Data Collection & Management: Data collection will be the responsibility of the study staff under the supervision of the PI. The PI will be responsible for ensuring the accuracy, completeness, legibility, and timeliness of the data reported.

All source documents will be completed in a neat, legible manner to ensure accurate interpretation of data. Hardcopies of the study visit worksheets will be provided for use as source document worksheets for recording data for each participant consented/enrolled in the study. Data recorded in the electronic case report form (eCRF) derived from source documents will be consistent with the data recorded on the source documents.

Clinical data (including AEs) and clinical laboratory data will be entered into secure study databases, if needed. The data system includes password protection and internal quality checks, such as automatic range checks, to identify data that appear inconsistent, incomplete, or inaccurate. Clinical data will be entered directly from the source documents.

Only authorized study staff will have access to study data.

Sample Size Determination: The sample was determined based on the medium-large effects found in our previous work and work by Klosky et al. and is sufficient to find similar sized effects; thus our proposed sample size will enable us to detect effect sizes previously found in the literature^{26,54-56}.

A sample size of n=20 per group will provide 80% power to detect large effect sizes of w=.45 for the chisquare analysis and d=.91 for the independent samples t-test. Because this is a pilot study, the focus will be on generating reliable effect size estimates for our primary outcome (FP uptake) comparing the intervention to standard care, rather than on statistical significance (using two-sided type I error rates (alpha values) of no more than .05). The proposed sample size is sufficient for gleaning this information.

Data Analysis Plan: Analyses will be conducted according to intent-to-treat methods, in which all randomized participants are included. Summary statistics will be calculated and qualitative methods used to evaluate the feasibility of recruiting and enrolling children.

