Chi-squared and t-tests will be used to evaluate primary and secondary outcomes. A chi-square analyses will examine the primary outcome of FP uptake (Y/N) as a function of treatment group status An independent samples t-test will examine whether the secondary outcomes of decision quality (numerical score on the BSDQ and family communication (numerical score on the PACS and difference scores on the PACS for AYA and parents) change between 1-month and 1-year follow-ups. Pearson's r correlations will be run to see if FP uptake (Y/N) is related to decision quality or family communication.

The two groups (intervention and control) will be examined in an *exploratory* manner to assess potential differences in factors known to affect FP decisions such as demographics (e.g. age), urgency to start treatment, knowledge, provider recommendation, and parent recommendation, as well as novel factors such as quality of parent-child communication. We will also examine these baseline factors as covariates within an analysis of covariance to see if might have a substantial impact on our effect size estimates for the larger RCT.

Quality Control of Data: Internal quality management of study conduct, data collection, documentation and completion will be conducted, under the direction of the PI. Quality control (QC) procedures will be implemented as follows:

- Informed consent: Study staff will review both the documentation of the consenting process as well as a percentage of the completed consent documents. This review will evaluate compliance with GCP, accuracy, and completeness. Feedback will be provided to the study team to ensure proper consenting procedures are followed.
- Source documents and the electronic data: Some data will be initially captured on source documents and will ultimately be entered into the study database. Some data will be entered directly into an electronic data capture system. To ensure accuracy of data initially captured on source documents, site staff will compare a representative sample of source data against the database, targeting key data points in that review. Some data will be entered directly into study databases. Electronic databases will be programed to alter study staff and/or participants of out of range values and/or potential errors.

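### The plan sets no unit of analysis for BSDQ and PACS: families are randomised and up to three relatives each give scores, so a t-test that combined relatives would be anti-conservative

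*Combined protocol and SAP*

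**What the plan says.** - **Randomised unit.** Section 6.0, Study Design: "Families will be randomized (1:1) to either receive" standard care or standard care plus the intervention.
- **Who gives scores.** Section 6.0, Visit 2, gives both scales to the AYA and both parents. For the PACS, "AYA will rate communication with both mother and father", so one AYA can supply two ratings. Section 12.0: "This study will enroll 40 male AYAs and 70 caregivers".
- **Who is analysed.** Section 17.0 specifies intent-to-treat, "in which all randomized participants are included". Sections 6.0 (Risk Minimization) and 29.4 count patients and parents alike as participants, each with a study ID.
- **Test.** Section 17.0: "An independent samples t-test will examine whether the secondary outcomes of decision quality". The sentence goes on to PACS scores and PACS difference scores for AYAs and parents. The contrast it names is change between the 1-month and 1-year follow-ups; it does not mention arm.
- **Hypotheses.** Section 2.0 states the secondary hypotheses as intervention families against control families.
- **Sizing.** Section 17.0: "A sample size of n=20 per group will provide 80% power" for, among others, "d=.91 for the independent samples t-test".

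The documents contain no mixed model, GEE, cluster-robust variance, family mean or designated main informant. The Pearson correlations and exploratory analysis of covariance are also given without a unit of analysis.

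**The concern.** An independent-samples t-test takes every score as a separate piece of information. A son and two parents rating the same decision, or the same relationship, are likely to give correlated scores, and so are one AYA's ratings of his mother and of his father. Treatment is also assigned to the whole family, so this correlation adds directly to the variance of the difference between arms. A test that counts people instead of families then has standard errors that are too small.

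At stake are the decision-quality and communication results. A pilot could report a benefit that its data do not support, or carry effect estimates with false precision into the planning of the larger RCT that Section 17.0 mentions.

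**Working it through.** **1. The plan's own power figure.** Inputs (Section 17.0): n=20 per arm, d=0.91, two-sided 0.05. Noncentral t with 38 degrees of freedom and noncentrality 0.91 × √(20/2) = 2.88 gives power of 80.1%, so the stated 80% reproduces. With 55 independent scores per arm, power at d=0.91 would be 99.7%, and the effect detectable with 80% power would be d=0.54. The sizing therefore fits one score per family per test.

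**2. The number of people.** 40 + 70 = 110 respondents (Section 12.0), or about 55 per arm: 20 AYAs and 35 caregivers. Take one family per AYA and at most two caregivers per family (Section 6.0 speaks of both caregivers). Then 70 caregivers from 40 families means at least 70 − 40 = 30 families supply two. A single test of all parents' scores would therefore contain correlated pairs.

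**3. Design effect.** Assumed mix per arm: 15 families with two caregivers and 5 with one (15 × 2 + 5 × 1 = 35). Weighted family size m′ = Σm²/Σm:
- caregivers only: (15 × 4 + 5 × 1)/35 = 65/35 = 1.857
- AYA and caregivers: (15 × 9 + 5 × 4)/55 = 155/55 = 2.818

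DE = 1 + (m′ − 1) × ICC. The actual type I error of a nominal 5% test is 2 × [1 − Φ(1.96/√DE)], and the confidence interval has 1/√DE of its proper width. The documents give no ICC; 0.3–0.5 is assumed, with the same value for every pair of relatives.

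| Scores in one test | ICC | DE | Type I error | Interval too narrow by |
|---|---|---|---|---|
| Caregivers only | 0.3 | 1.257 | 8.0% | 11% |
| Caregivers only | 0.5 | 1.429 | 10.1% | 16% |
| AYA and caregivers | 0.3 | 1.545 | 11.5% | 20% |
| AYA and caregivers | 0.5 | 1.909 | 15.6% | 28% |

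Simulated null trials agree. Caregivers only: 8.1% and 10.4% (8,000 trials per setting). All members: 11.4% and 15.8% (40,000 trials per setting). Over ICC 0.1 to 0.7 the formula gives 6.0% to 12.1% for caregivers only and 7.1% to 19.4% for all members.

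**4. One score per family.** In the same 40,000-trial simulations, using the family mean or the AYA's score alone, type I error was 4.9% to 5.1% at every ICC from 0 to 0.7.

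**The case against.** A reader might infer that the plan pools relatives' scores, so that false positives will rise. The documents do not say so. The intent-to-treat sentence fixes who is analysed; it does not make each relative a separate observation in one test. The n=20 sizing points the other way, to one score per family. One test per informant role (AYA, mother, father) would not breach independence.

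The quoted sentence also describes 1-month to 1-year change, not an arm comparison. Read literally, it applies an independent-samples test to the same people's two scores, which is conservative: simulated type I error was 2.0%, 0.6% and 0.03% at correlations 0.3, 0.5 and 0.7 with 40 people. That is the opposite direction.

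Finally, these are secondary outcomes in a pilot that puts estimation ahead of significance, and the sizes above rest on assumed correlations, family mix and complete response.

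Most of this stands, and it makes the inflation conditional. It does not remove the gap. The plan has no rule for reducing about 55 participants per arm to 20 scores. For the PACS difference scores it names AYAs and parents, not mothers and fathers, and Section 10.0 admits grandparents and same-sex parents, so a mother/father split would need its own rule. The emphasis on estimation is stated for FP uptake, and intervals that are too narrow harm estimation as well as testing.

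**Conclusion.** The plan leaves the unit of analysis for BSDQ and PACS undefined and makes no provision for within-family correlation, although the family is the randomised unit. Its power figure holds only with one score per family per test.

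If two caregivers per family entered one between-arm t-test, type I error would be about 8–10%; if AYA and caregiver scores were combined, about 11–16%. Intervals would be too narrow by 11–16% and 20–28% respectively. These figures assume pooling, a between-arm contrast, ICC 0.3–0.5 and the 15/5 family mix. Pooling is a possibility that the text leaves open, not something it states. Under these null calculations pooling affects precision and does not bias the estimated difference. FP uptake has one value per AYA and is unaffected.

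**What to change.** In the Data Analysis Plan (Section 17.0):

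1. State that secondary outcomes are compared between arms with one score per family per test. Analyse AYA and caregiver informants separately and designate one as main, for example the AYA's own score, to which the n=20 per group power applies. A main informant also limits multiplicity: two or three independent tests at 0.05 would give 1 − 0.95² = 9.8% or 1 − 0.95³ = 14.3%.
2. Analyse caregiver scores, and the AYA's separate mother and father PACS ratings, as a family mean or in a linear mixed model with a family random intercept and small-sample degrees of freedom. The mixed model keeps the parent-specific information that averaging loses.
3. Replace the 1-month versus 1-year contrast with the between-arm contrast of Section 2.0, at the time points of Section 4.0. In doing so, reconcile the 1-year PACS endpoint in Section 4.0 with Section 6.0, which lists no PACS at Visit 3.
4. Apply the same unit to the Pearson correlations.

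The cost is analysis-plan wording, simple modelling and slightly wider confidence intervals than a person-level test would show. Sample size and data collection need not change for points 1, 2 and 4. Point 3 touches data collection only if the 1-year PACS endpoint is kept.

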Aims: This randomized clinical trial (RCT) will test the feasibility, acceptability, and preliminary efficacy of a novel family-centered, psychoeducational intervention with known and newly identified factors to improve fertility preservation (FP) uptake, decision quality, and family communication among male adolescents and young adults (AYAs) newly diagnosed with cancer. The primary aim of this project is to examine preliminary efficacy of the psychoeducational intervention with regard to FP uptake.

Hypotheses: The primary hypothesis is that compared to standard of care control group (routine fertility consult at diagnosis, n=20), AYAs in the intervention arm (routine fertility consult at diagnosis + FP Decision Tool and Facilitated Conversation by trained interventionist; n=20) will have higher rates of FP uptake. The secondary hypotheses are that families in the intervention group will report better FP decision quality and report improvements in family communication, compared to those in the control arm.

Rationale: Nearly 9,000 males under age 20 are diagnosed with cancer in the U.S. each year¹. With 5-year survival rates exceeding 80%, the population of male childhood cancer survivors is now close to 200,000². Unfortunately, approximately 50% of male survivors have impaired fertility³⁻⁵, which can impede psychosexual development and diminish quality of life (QoL)⁶. Sperm banking is an established and effective method of FP for pubertal males⁷, yet only 25% of eligible adolescents bank sperm prior to

treatment⁸⁻¹². As these AYAs complete therapy and approach their reproductive years, many survivors and their parents *regret* missed opportunities for FP and report *distress* about potential infertility¹³⁻¹⁶.

Significant knowledge gaps exist with regard to pediatric FP:

- 1. Most research examining FP decisions has focused on females^{17,18}, despite a higher prevalence of cancer and treatment-related infertility in males¹⁹;
- 2. Many studies examining FP predictors have been conducted years after therapy and are subject to recall bias^{15,20};
- 3. Little attention has been paid to *decision quality* (satisfaction/regret) soon after FP decisions are made;
- 4. Although parents make most healthcare decisions even in late adolescence/young adulthood, *family factors* including parent-child communication about FP, have not been examined.

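### The planned correlations of FP uptake with decision quality and family communication do not condition on randomised arm, so r is shifted away from zero if the intervention moves both variables

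*Combined protocol and SAP*

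**What the plan says.** The Data Analysis Plan in Section 17.0 gives these analyses one sentence, which says that Pearson "correlations will be run to see if FP uptake (Y/N) is related to decision quality or family communication". Arm, visit and respondent are not mentioned. Earlier in the same paragraph, the chi-square test of uptake is defined by treatment group. The section opens by committing to intent-to-treat analysis with every randomised participant included. The only covariate adjustment is an analysis of covariance on baseline factors, meant to inform effect sizes for a larger trial. It is not tied to the correlations.

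The Hypotheses in Section 2.0 state that AYAs in the intervention arm "will have higher rates of FP uptake", and that "families in the intervention group will report better FP decision quality and report improvements in family communication". Allocation is by family (Section 6.0, Study Design: "Families will be randomized (1:1) to either receive" one of the two arms).

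On size, Section 17.0 states: "A sample size of n=20 per group will provide 80% power to detect large effect sizes of w=.45 for the chisquare analysis and d=.91". The second figure belongs to the t-test, and the error rate is set by "using two-sided type I error rates (alpha values) of no more than .05". No figure is given for the correlations.

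**The concern.** Under the trial's own hypotheses, randomised arm is a common cause of the two variables being correlated. A single r across both arms then combines two things: any link between banking and the score among families treated alike, and the product of the two treatment effects. The second part is present even when the first is zero. Where a higher score means a better result, it pushes r upward, towards the finding that those who banked were more satisfied or communicated better.

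This sentence is the plan's only stated quantitative analysis of that question. At stake is how the result will be read. A positive r could be taken as evidence that banking goes with better decisions, when it shows only that the intervention did two things at once. The plan puts estimation ahead of significance, so a displaced estimate matters even where it does not reach p<.05.

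**Working it through.** **Inputs.**
- 20 per arm, 40 in total, 1:1; w=.45, d=.91; two-sided alpha .05 (Sections 6.0 and 17.0).
- Control uptake of 25% is an assumption taken from the background in Section 2.0 ("only 25% of eligible adolescents bank sperm"). The plan states no expected uptake for either arm.
- Also assumed: normal scores with equal variance, one score per AYA, no dropout, and no association between uptake and score within either arm.

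**1. The plan's own power figures.**
- Chi-square: noncentrality 40 × .45² = 8.1 on 1 df gives 81.2% power (exactly 80% at w=.443).
- t-test: noncentrality .91 × √10 = 2.88 on 38 df gives 80.1% power.

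Both agree with the stated 80%.

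**2. Correlation induced by arm alone.** Let uptake be p₁ in control and p₂ in intervention, with mean p̄, and let the score differ by d standard deviations. If the two are independent within arm and allocation is 1:1:
- covariance = (p₂ − p₁) × d / 4
- variance of uptake = p̄(1 − p̄); variance of score = 1 + d²/4
- w = (p₂ − p₁) / (2√[p̄(1 − p̄)])

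Hence r = w × d / √(d² + 4).

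At the plan's values: .45 × .91 / √(.91² + 4) = .4095 / 2.197 = **.186**.

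**3. How often a nominal 5% test rejects.** By Fisher's z with n=40: atanh(.186) × √37 = 1.15, so the rejection probability is about 1 − Φ(1.96 − 1.15) = 21%. The smallest |r| significant at n=40 is 2.024 / √(38 + 2.024²) = .312, so the induced r is on average below the threshold.

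**4. Simulation (100,000 trials of 20+20 per row).** With 25% in control, w=.45 corresponds to 69.9% in the intervention arm, a value solved from w and not stated in the plan.

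| Uptake, control v intervention | w | d | r by formula | Mean r, all participants | Rejection, all participants | Rejection, arm-adjusted |
|---|---|---|---|---|---|---|
| 25% v 69.9% | .45 | .91 | .186 | .19 | 22% | 5.0% |
| 25% v 69.9% | .45 | .5 | .109 | .11 | 10% | 5.1% |
| 25% v 50% | .258 | .5 | .063 | .06 | 7% | 5.1% |
| 25% v 69.9% | .45 | 0 | 0 | .00 | 5.0% | 5.1% |
| 25% v 25% | 0 | .91 | 0 | .00 | 4.9% | 5.0% |

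The arm-adjusted r averages .00 in every row. The last two rows show that an effect on uptake alone, or on the score alone, induces nothing. At w=.20 and d=.2 the formula gives r=.02, with rejection still about 5%.

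**The case against.** Five points can be made in the plan's defence.

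- **The plan does not say that the arms are pooled.** True: it is silent. Pooling is still the natural reading, because the sentence gives a plain Pearson r and the section includes all randomised participants. Following the method as written produces the unadjusted r.
- **The headline figures use large effects.** This stands. The plan gives w=.45 and d=.91 as detectable effects, not expected ones, and describes earlier findings as medium to large. The smaller scenarios belong beside the headline.
- **An unadjusted r is a valid description of the marginal association.** This also stands. The fault lies in reading it as a link between banking and the score apart from arm. The stated purpose, to see whether the two are related, invites that reading without saying which association is meant.
- **The analysis ranks low.** The correlation is neither an endpoint (Section 4.0) nor a hypothesis (Section 2.0). It has no power statement or decision rule, and the plan says that significance is not its focus. All of this limits the importance of the point.
- **Other planned work bears on the question.** Interviews are coded for themes and the FP Decision Survey guides analyses (Section 6.0). These are relevant but do not replace a quantitative estimate.

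A reader might infer that the correlation will show an association whenever the intervention works. The documents do not support that. Uptake and the scores are separate primary and secondary hypotheses, and success on uptake alone leaves r at zero. Even at the large effects with both moved, about 78% of trials would not reach significance.

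**Conclusion.** The point holds for a supporting analysis and is a cheap improvement. The correlations are specified without conditioning on arm, although the trial hypothesises that arm affects both variables. If both effects occur, r over all participants is displaced: by about .19 at w=.45 and d=.91 (rejection 21–22% against a nominal 5%), by about .11 at w=.45 and d=.5 (10%), and by about .06 at 25% v 50% with d=.5 (7%). If only one variable moves, there is no displacement.

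The formula rests on 1:1 allocation and no within-arm association. The simulated rates also rest on the assumed 25% control uptake, normal scores and complete data. It would be wrong to infer that the trial's main result is compromised: the chi-square comparison of uptake between arms does not use these correlations.

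**What to change.** Replace the unadjusted Pearson r with the arm-adjusted (partial) correlation: regress the score on uptake and arm, and report the partial r with its confidence interval. Fit one model per informant at each visit where the score is collected, and give the within-arm correlations descriptively.

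The visit restriction matters. Section 6.0 lists the BSDQ at Visits 2 and 3 but lists no PACS at Visit 3, although Section 4.0 names a 1-year PACS change as a secondary endpoint. On the current schedule the PACS models can be fitted at Visit 2 only.

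The cost is a one-sentence change, one degree of freedom per model (37 residual instead of 38 with 40 complete pairs) and no new data. The number of analyses is already implied by the measures: up to 3 informants × 2 visits = 6 for the BSDQ, and for the PACS up to 4 ratings (the AYA's of each parent, and each parent's of the son) × 3 scores = 12. Adjustment does not add to these, but with 40 AYAs they should be presented as estimates. Adjusting for arm removes only the part due to treatment. Banking is not itself randomised, so the adjusted r remains observational.
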